7.7.2. Sensitivity Analyses of the Primary Efficacy Endpoint

To evaluate the robustness of the primary analysis approach, sensitivity analyses, e.g., placebo-based imputation and tipping point analysis will be performed. In placebo-based imputation, missing pVO₂ from subjects who discontinued from aficamten treatment or missing pVO₂ from subjects from the placebo arm will be imputed based on the model that is constructed using observed pVO₂ data from the placebo arm. Missing pVO₂ from subjects who remained on aficamten treatment will be imputed based on the model that is constructed using observed pVO₂ data from aficamten arm. Tipping point analysis will be performed by applying a range of negative shift to adjust the imputed value of missing pVO₂ in aficamten group. If there are 10% or more missing data and/or 5% or more subjects missing data due to reason related to IP, the primary analysis will have the missing data imputed using placebo-based imputation.

The tipping point can be identified while the result is no longer statistically significant. Clinical judgment will be applied to evaluate the plausibility of the assumptions underlying this tipping point.

In addition, sensitivity analysis to evaluate COVID-19 impact will be performed by repeating the primary analysis after setting the Week 24 CPET to missing from subjects who are impacted by COVID pandemic.

Another sensitivity analysis is to fit a repeated measures mixed model to pVO₂ baseline and Week 24 data. The model includes stratification factors, visit, stratification by visit, and a numeric covariate which equals 0 for both treatment groups at baseline and equals 0 for placebo at Week 24 and equals 1 for aficamten group at Week 24. The primary treatment comparison is for the numeric covariate for treatments which corresponds to the treatment difference at week 24 in a specification for which there is no treatment difference at baseline.

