9.4.2. Primary Endpoint(s)

The primary endpoint of the study is change in pVO_2 by CPET from baseline to Week 24.

The primary estimand is the difference in means of the change from baseline to Week 24 in pVO_2 between CK-3773274 and placebo for the target population of potentially treatable CK-3773274 patients despite intercurrent events after a first dose. Missing data will be imputed using multiple imputation method under the missing at random (MAR) assumption. The

distribution of missing CPET data at Week 24 and the reasons for the missing data will be tabulated in the FAS. The primary analysis of the primary endpoint will use an ANCOVA model with treatment group, randomization stratification factors, baseline pVO₂ and baseline weight as covariates in the FAS. Sensitivity analyses will be performed by repeating the primary analysis examining assumptions that data are not missing at random: missing pVO₂ from patients who discontinued CK-3773274 treatment or missing pVO₂ from patients from the placebo arm will be imputed based on the model that is constructed using observed pVO₂ data from the placebo arm. Missing pVO₂ from patients who remained on CK-3773274 treatment will be imputed based on the model that is constructed using observed pVO₂ data from the CK-3773274 arm. The LSMs, LSM treatment difference, and the standard error from each imputed dataset will be combined using Rubin's rules to produce an overall LSM estimate of the treatment difference, its 95% confidence interval, and p-value.

Other sensitivity analyses and the details will be included in the SAP.

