5.8. Handling of Missing Data

5.8.1. Missing Efficacy Endpoints

For the primary endpoint, missing data will be imputed under missing at random (MAR) assumption and all observed and imputed missing pVO₂ assessments will be included in the primary analysis of the primary endpoint. Missing secondary CPET endpoints will be handled the same as for the primary endpoint. Missing response for patient reported outcomes will be handled as described in [Section 11.1](#).

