- COVID-19 related intercurrent events e.g., subjects' decision to early terminate from the study due to the COVID-19 precautions, site closures, hospitalization due to COVID-19, or COVID-19 symptoms preventing subjects from coming to the Week 24 visit.

CPET data deemed to be invalid by the CPET core lab will be treated as missing CPET data in the analysis. CPET core lab flags the CPET results as invalid when there are:

- Technical equipment failure during CPET (i.e., air leak/lack of proper equipment utilization such as missing nose clip leading to lack of capture of gas exchange data)
- Transient non-cardiac issues that precluded conduct of the exercise study (as defined by inability to turn the pedals during the warm-up period for at least 3 min)
- CPET MOP-major CPET process deviation can impact one or more CPET variables.

Missing data as a result of an invalid assessment by the CPET core lab cab will be considered as missing at random.

Missing pVO₂ at Week 24 regardless of type of intercurrent events will be imputed using multiple imputation methodology under the MAR assumption for the primary analysis of the primary estimand. Missing Week 24 CPET is expected to be low. Patients will be followed according to the schedule of activities in the protocol from randomization through the date of final visit irrespective of whether the patient is continuing to receive IP unless the patient has discontinued prematurely from the study or withdrawn consent. The protocol allows up to 4 weeks extension of Week 24 in the event that the subject is temporarily unable to exercise due to an AE e.g., ankle sprain, upper respiratory infection etc. or due to equipment malfunction to ensure post randomization CPET data collection. Missing Week 24 CPET due to intercurrent events i.e., non-CV AEs or COVID-19 related intercurrent events can be considered as MAR. Death event is expected to be very rare given the patient population and the duration of the treatment in this study. Assume patients' risk of death event or hospitalization due to HCM symptom and other CV AEs is balanced between treatment groups, missing data due to this type of intercurrent events for the primary estimand will be imputed as MAR.

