Table 6 summarizes the primary and secondary efficacy endpoints and planned analysis method.

Table 6: Endpoint Summary Table

Endpoint	Primary Analysis Method	Sensitivity/Subgroup Analysis	COVID-19 Related Analyses
Primary Endpoint: Change in pVO ₂ on CPET from baseline to Week 24			
Primary estimand ¹	Missing data will be imputed using multiple imputation method (Section 7.7.1). Complete dataset will be analyzed using an ANCOVA model with fixed effects of treatment, randomization stratification factors baseline pVO ₂ value and baseline body weight	
Sensitivity analysis
 
 • ANCOVA model will be repeated with missing data from subjects who discontinued aficamten treatment as if the aficamten subjects were in the placebo arm • Tipping point analysis 
Supportive analysis
 
 • Mixed model with numeric covariate as 0 for baseline and placebo group at Week 24 and 1 for aficamten group at Week 24, visit, stratification factors and stratification factors by visit as fixed term. unscheduled covariance structure will be specified. • Multivariate ANCOVA model to evaluate treatment by covariates interaction; ANCOVA model with significant covariates per model selection 
Subgroup analyses for variables in Section 7.5
	
 • Repeat the primary analysis after setting Week 24 pVO₂ to missing from subjects who were impacted by COVID pandemic • Summarize the number of subjects infected (positive COVID-19 test with or without symptoms) prior to Week 24 CPET.
Secondary estimand	ANCOVA model with fixed effects of treatment, randomization stratification factors baseline pVO ₂ value and baseline body weight.	Subgroup analyses for variables in Section 7.5	

Table 6: Endpoint Summary Table (Continued)

Endpoint	Primary Analysis Method	Sensitivity/Subgroup Analysis	COVID-19 Related Analyses
Secondary Endpoints			

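### The SAP makes placebo-based imputation primary at a missing-data trigger, while four other places keep MAR primary without condition; the sample code implements neither rule

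*SAP*

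**What the plan says.** The switch is one sentence under the sensitivity heading, SAP Section 7.7.2, which opens: "If there are 10% or more missing data and/or 5% or more subjects missing data due to reason related to IP, the primary analysis will". It has two limbs: at least 10% of data missing, and/or at least 5% of subjects missing data for a reason related to investigational product (IP). If it is met, "the primary analysis will have the missing data imputed using placebo-based imputation". The same section describes that method. Missing values of placebo patients and of patients who stopped aficamten come from a model built on observed placebo-arm data, and missing values of patients still on aficamten come from observed aficamten data.

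Elsewhere the primary method has no condition:

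- SAP 5.8.1: "For the primary endpoint, missing data will be imputed under missing at random (MAR) assumption".
- SAP 7.7.1: missing Week 24 pVO2 "regardless of type of intercurrent events will be imputed using multiple imputation methodology under the MAR assumption for the primary analysis of the primary estimand".
- SAP Table 6: multiple imputation by reference to 7.7.1. Under sensitivity analysis it lists: "ANCOVA model will be repeated with missing data from subjects who discontinued aficamten treatment as if the aficamten subjects were in the placebo arm".
- Protocol 9.4.2: "Missing data will be imputed using multiple imputation method under the missing at random (MAR) assumption". The placebo-based method follows as a sensitivity analysis: "Sensitivity analyses will be performed by repeating the primary analysis examining assumptions that data are not missing at random".

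Appendix 11.5 gives the placebo-based method as three steps. It forms one dataset from placebo patients plus subjects who did not complete treatment, runs the primary imputation model on each dataset separately, and combines the results. That primary model contains treatment group (SAP 7.7.1 and the sample code).

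**The concern.** Above the trigger, a programmer following 7.7.2 and one following 7.7.1, Table 6 or the protocol would run different confirmatory tests. SAP Table 4 stops all testing if Step 1 fails. Total workload (Step 11) follows the same imputation approach, and the primary-endpoint subgroup analyses reuse the primary imputations.

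The 10% limb equals the missing rate assumed in the sample size, so it is not remote under the plan's own planning figure. The IP-related limb has no derivation. The eCRF reasons for a missing CPET in SAP 7.7.1 include adverse events but no IP-related category. Causality is recorded for each adverse event (Protocol 8.4.1.4), but nothing links it to the missing test.

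The appendix raises a second problem. Table 5 expects some patients who stop treatment to have a Week 24 value. If such aficamten patients are in the pooled dataset, the treatment term is estimated from them alone, and missing discontinuers are imputed around those few values. If there are none, the term cannot be estimated in that dataset.

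**Working it through.** **Inputs from the documents (Protocol 9.2, SAP 3.3.1).** Difference 1.5 mL/kg/min, SD 3.5, 270 patients 1:1, 10% missing, two-sided alpha 0.05.

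**Stated power.** n per arm = 135 × 0.9 = 121.5. Noncentrality = 1.5 / (3.5 × √(2/121.5)) = 3.34. The noncentral t gives 0.914, so the claim of more than 90% reproduces.

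**Chance that the trigger fires.** With the pooled full analysis set as denominator, 10% of 270 is 27 and 5% of 270 is 13.5, so 14. Binomial probabilities:

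| True rate | 10% limb: P(≥27 of 270) | | True rate | IP-related limb: P(≥14 of 270) |
|---|---|---|---|---|
| 10% | 0.530 | | 5% | 0.483 |
| 9% | 0.312 | | 4% | 0.196 |
| 8% | 0.137 | | 3% | 0.035 |
| 7% | 0.040 | | | |
| 5% | 0.0005 | | | |

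**MAR against placebo-based imputation as 7.7.2 describes it.** Imputing off-treatment patients at the placebo level shrinks the difference:

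- 7 of 135 aficamten patients: 1.5 × (1 − 7/135) = 1.42.
- 14 of 135: 1.5 × (1 − 14/135) = 1.34.

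An ANCOVA simulation used 14 missing per arm, 100 imputations, Rubin's rules and 8,000 trials per scenario (Monte Carlo SE about 0.003). Two inputs are assumptions: the baseline-to-change correlation r, and how many of the 14 missing aficamten patients were off IP. Placebo-based power, with MAR in brackets:

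| r | 0 off IP | 7 off IP | 14 off IP |
|---|---|---|---|
| 0 | 0.912 (0.912) | 0.896 (0.915) | 0.866 (0.908) |
| 0.2 | 0.924 (0.924) | 0.904 (0.920) | 0.879 (0.917) |
| 0.4 | 0.952 (0.952) | 0.936 (0.947) | 0.921 (0.948) |

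MAR is significant and placebo-based is not in 1.2–1.9% of trials with 7 off IP and 2.7–4.2% with 14. Under the null (all 14 off IP, r = 0.2), rejection is 0.051 for MAR, 0.026 for placebo-based and 0.051 for either. The imputation model omitted post-randomization NYHA class and LVOT gradient, which could reduce the dilution.

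**Appendix 11.5 against the 7.7.2 text.** There were 4,000 trials, r = 0.2 and 14 missing per arm. Here k is the assumed number of off-IP aficamten patients with an observed Week 24 value. The SE under the text is 0.44.

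| Missing aficamten patients off IP | Code SE, k=1 | k=2 | k=4 | k=7 |
|---|---|---|---|---|
| 14 | 0.59 | 0.52 | 0.48 | 0.47 |
| 7 | 0.49 | 0.47 | 0.45 | 0.45 |

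A rough hand check for 14 off IP and k = 2: residual SD = 3.5 × √(1 − 0.04) = 3.43. The treatment term has SE about 3.43 × √(1/2 + 1/121) = 2.45. It carries weight 14/135 = 0.104, so it adds about 0.25. Then √(0.44² + 0.25²) = 0.51, close to the simulated 0.52.

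At k = 2:

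| Off IP | Power, text | Power, code, if the k patients lost the effect | Power, code, if they kept it | Conclusions differ (lost / kept) |
|---|---|---|---|---|
| 14 | 0.87 | 0.72 | 0.81 | 16.8% / 11.3% |
| 7 | 0.90 | 0.86 | 0.89 | 6.1% / 3.7% |

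The estimate can move too. If the k patients kept the effect, the code gives about 1.49, against 1.33 (14 off IP) or 1.41 (7 off IP) under the text. The code then largely undoes the conservatism that the switch is meant to bring.

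**The case against.** The passages can be read as one rule: MAR by default, with 7.7.2 as a specific numeric exception. The 7.7.1 phrase about intercurrent events concerns their type, not the amount of missing data, and Protocol 9.4 calls itself a summary that the SAP will detail. The effect is also small. At a true 10% missing rate, 0.53 × 1.2% to 0.53 × 4.2% is about 0.6% to 2.2% of trials; SAP 7.7.1 expects missingness to be low, and at 5% missing the 10% limb almost never fires. The largest code-versus-text gaps need every missing aficamten patient to be off treatment and very few retrieved. With 7 off IP and 4 to 7 retrieved, disagreement is 1.8–3.7%. The appendix is headed as sample code.

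The points on size stand and should temper how the numbers are read. The default-plus-exception reading does not settle the conflict. Table 6 and Protocol 9.4.2 assign placebo-based imputation to the sensitivity analyses, and no other section mentions the trigger. Nor can the SAP be taken as the later refinement: Protocol Amendment 04 (8 December 2023) postdates SAP Version 2 (effective 9 October 2023) and still has MAR without condition. The appendix may be illustrative, but it is the only operational specification of a method that can become primary.

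**Conclusion.** The concern holds. Once the trigger is met, the plan gives two incompatible definitions of its primary test, and the appendix describes a model that is not placebo-only. The chance of meeting the 10% limb is about even at the planned missing rate and negligible at 5%. Given that it is met with 14 missing per arm, the choice between MAR and placebo-based imputation changes the conclusion in about 1% to 4% of trials if half or all of the missing aficamten patients had stopped treatment, and not materially if none had. The choice between code and text can matter more, 4% to 17% with two retrieved patients and less as retrieval improves. These percentages rest on assumed off-treatment shares, correlations and retrieval numbers, which the documents do not give. The direction of the switch is conservative and type I error is not at issue. The point must be fixed because the confirmatory analysis has to be uniquely defined before lock, whatever the size of the effect.

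**What to change.** State one primary imputation rule in the same terms in SAP 5.8.1, 7.7.1, 7.7.2 and Table 6 and in Protocol 9.4.2. There are two ways to do it.

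1. **Keep the switch** and cross-reference it in each place. Define the denominator as the pooled full analysis set, with CPETs ruled invalid by the core laboratory counted as missing. Derive the IP-related limb from recorded adverse-event causality, assessed blinded before database lock. Cost: a note that the stated power assumes no dilution and may fall somewhat below 90% at about 10% missing or more if most missing aficamten patients had stopped treatment.
2. **Remove the switch**, keep MAR primary, and always report the placebo-based and tipping-point analyses. Cost: a prespecified conservative safeguard is lost, so those two analyses must carry the question.

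In either case, rewrite the Appendix 11.5 steps so that the model for placebo patients and aficamten discontinuers is fitted to observed placebo-arm data only, without a treatment term.

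The changes are wording and sample code. Design, sample size and data collection are unaffected.

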7.7.3. Subgroup Analyses for the Primary Endpoint

Subgroup analyses will be performed by including the subgroup effect and subgroup by treatment interaction terms to the primary ANCOVA model for the primary endpoint. For subgroup analysis for the primary estimand, missing data imputed in the primary analysis will be used in the subgroup analyses. Only summary statistics will be presented for the subgroup level when the number of subjects in either treatment arm is ≤ 15 at this level. LSM estimate of the treatment difference, 95% confidence intervals for the mean treatment difference and nominal p-values will be provided for each subgroup level.

7.7.4. Supportive Analyses for the Primary Endpoint

To explain heterogeneity or identify treatment effect modifiers from the baseline characteristics, covariates used to define pre-specified subgroups and these covariates by treatment interaction

terms will be included in the ANCOVA model as supportive analysis. Global test of covariates by treatment interactions will be performed.

Stepwise model selection method will be used based on the stay or entry level of 0.05 to evaluate significant baseline covariates impact on the primary endpoint. ANCOVA model will be repeated by adjusting for the significant baseline covariates. Covariates measured as continuous will be introduced to the model as continuous variable. These analyses will be based on observed data.

The normality assumptions of the ANCOVA model will be investigated graphically. The scaled residuals will be examined. A supportive analysis will be performed after transforming pVO₂ data into ranks if greater than 5% of patients have an extreme change from baseline value at Week 24. Extreme values in the pooled data are defined as observations outside of Tukey's outer fences, i.e. observations that are less than the 25% quartile – 3 times the inter quartile range or greater than 75% quartile + 3 times the inter quartile range. Ranks will be applied to all changes from baseline data after the imputation step. Baseline data will be ranked separately.

The secondary estimand will be analyzed using the same primary analysis ANCOVA model for the primary estimand. Subgroup analysis for the secondary estimand will be performed using the same ANCOVA model for the subgroup analysis for the primary estimand.

7.8. Analysis of the Secondary Efficacy Endpoints

The secondary endpoint(s) of the trial are:

- Change in KCCQ-CSS from baseline to Week 12 and Week 24
- Proportion of patients with ≥ 1 class improvement in NYHA Functional Class from baseline to Week 12 and Week 24
- Change in post-Valsalva LVOT-G from baseline to Week 12 and Week 24
- Proportion of patients with post-Valsalva LVOT-G <30 mmHg at Weeks 12 and 24
- Total duration of SRT eligibility during the 24-Week treatment period in patients who were SRT eligible at baseline
- Change in total workload during CPET from baseline to Week 24

7.8.1. Analysis of the Secondary Efficacy Endpoints

1. Change in KCCQ-CSS from baseline to Week 12 and Week 24

The primary analysis for change in KCCQ-CSS from baseline to Week 12 and 24 will be performed using a MMRM model with baseline as covariate, randomization stratification factors, visit, treatment group, and interaction terms of treatment by visit and baseline by visit. An unstructured covariance matrix will be specified. All data observed up to Week 24 post randomization will be included in the model. Estimates for endpoints at Week 12 and Week 24 will be obtained from the LS Means estimate at visit of Week 12 and 24 from the model.

If there are >10% difference in baseline KCCQ CSS across regions, treatment by visit and region, baseline by visit and region will be included in the model. Treatment effect at each visit

week will be estimated from the interaction terms of treatment by visit by region, with coefficients for each region determined by proportion of patients evaluated in each region.

Sensitivity analysis based on multiple imputation with one hundred invocations will be performed. First the intermittent missing data will be imputed using the Markov Chain Monte Carlo (MCMC) method under MAR assumption. The imputation will be performed separately for each randomized treatment group and will include the following terms in the imputation model: region (for KCCQ only), endpoint observations from baseline up to Week 24. The monotone missing data will be imputed using the imputation model built from placebo group. 100 complete data sets will be generated and analyzed using the same model for the primary analysis of the change from baseline endpoint. The results from the 100 complete data sets will be combined using Rubin's combination rule for the inference.

Subgroup analysis will be performed using the primary analysis model MMRM model including additional effects of subgroup, subgroup by treatment and subgroup by treatment by visit interaction the model.

2. Change from baseline in post-Valsalva LVOT-G from baseline to Week 12 and Week 24

The analysis of this endpoint will follow the same specified above for change in KCCQ-CSS change from baseline to Week 12 and 24.

3. Proportion of patients with ≥ 1 class improvement in NYHA Functional Class at Weeks 12 and Week 24

For the proportion of patients with ≥ 1 class improvement in NYHA class at Week 12, Week 16 NYHA class will be used if Week 12 NYHA class is not available. Week 8 NYHA class will be used if Week 16 NYHA is not available. Patient will be considered as not achieving ≥ 1 improvement in NYHA class at Week 12 if no NYHA at Weeks 8, 12 and 16 is available. Similarly, Week 20 NYHA class will be used if Week 24 NYHA is not available. Patient will be considered as not achieving ≥ 1 improvement in NYHA class at Week 24 if Week 20 and Week 24 NYHA are not available. A sensitivity analysis will be performed by repeating Cochran–Mantel–Haenszel (CMH) test by assigning missing NYHA class at Weeks 12 and 24 as non-responders. Proportion of patients with ≥ 1 class improvement in NYHA class will be analyzed using CMH test stratified by randomization factors. The p-value and 95% CI will be obtained using exact method.

Subgroup analysis will be done by repeating the CMH test for each subgroup level without specifying stratifying by randomization stratification factors.

4. Proportion of patients with post-Valsalva LVOT-G < 30 mmHg at Weeks 12 and 24

For the proportion of patients with post-Valsalva LVOT < 30 mmHg at Week 12, Week 16 post-Valsalva LVOT will be used if Week 12 visit is performed but post Valsalva LVOT is not available. Week 8 post-Valsalva LVOT will be used if Week 16 is not available. Similarly, Week 20 post Valsalva LVOT will be used if Week 24 is performed but post Valsalva LVOT is not available.

Proportion of patients with post-Valsalva LVOT-G < 30 mmHg at Weeks 12 and 24 will be analyzed using Cochran–Mantel–Haenszel (CMH) test stratified by randomization factors. The p-value and 95% CI will be obtained using exact method.

Subgroup analysis will be done by repeating the CMH test for each subgroup level without specifying stratifying by randomization stratification factors.

- Total duration of SRT eligibility during the 24-Week treatment period in patients who were SRT eligible at baseline

Patient SRT eligibility will be assigned after data handling in case there are missing NYHA class or LVOT assessments. Intermittent missing NYHA or LVOT will be imputed follows the same imputing method for missing Week 12 or Week 24; e.g., impute Week 16 NYHA if Week 20 NYHA is available or use Week 12 NYHA if Week 20 NYHA is not available. Patient will be treated as SRT eligible if SRT eligibility can't be determined due to the missing NYHA class or LVOT assessments or clinical visits not performed after patient early terminates from the study.

Total duration will be calculated as the number of days patients are SRT eligible, from the date of the randomization until Week 24. Total duration will be 24 weeks if a patient remains SRT eligible at all visits from baseline until Week 24 (regardless of whether a patient is SRT eligible at Week 24 or not). Because the SRT eligibility status of a patient may change during the study conduct, only intervals during which the patient is SRT eligible, will be summed. The start of the interval is the time of randomization (or resumption of SRT eligible status), and the end of the interval is the date prior to the visit when the patient becomes SRT not eligible.

SRT (Y/N) Case #	Week 2	Week 4	Week 6	Week 8	Week 12	Week 16	Week 20	Week 24	Duration SRT Eligible (Weeks)
1	N	Y	Y	Y	N	N	Y	Y	12
2	Y	Y	N	N	Y	N	N	Y	10
3	Y	Y	N	N	N	N	N	N	6
4	Y	Y	N	N	Y	N	Y	N	14
5	Y	Y	N	N	Y	N	Y	Y	14

Total duration of SRT eligibility during the 24 Week of treatment period will be analyzed using an ANCOVA model includes treatment and randomization stratification factor beta blocker use/non-use as fixed effects and significant baseline characteristics as covariates. Stepwise model selection method will be used based on the default stay or entry level of 0.05 to evaluate significant baseline covariates. Sensitivity analysis of the SRT eligible endpoints includes repeating the same ANCOVA analysis the area under the curve calculated using the numeric value assigned to the SRT eligibility at each visit and treatment duration until Week 24, where SRT eligibility is assigned to value of 1 and SRT not eligible is assigned to value of 0.

- Change in total workload during CPET from baseline to Week 24

The primary and sensitivity analysis for the total workload will follow the same analysis approach for the primary estimand of the primary endpoint.

Subgroup analysis will be performed similarly as specified for the primary endpoint.

Table 6 summarizes the primary and secondary efficacy endpoints and planned analysis method.

Table 6: Endpoint Summary Table

Endpoint	Primary Analysis Method	Sensitivity/Subgroup Analysis	COVID-19 Related Analyses
Primary Endpoint: Change in pVO ₂ on CPET from baseline to Week 24			
Primary estimand ¹	Missing data will be imputed using multiple imputation method (Section 7.7.1). Complete dataset will be analyzed using an ANCOVA model with fixed effects of treatment, randomization stratification factors baseline pVO ₂ value and baseline body weight	
Sensitivity analysis
 
 • ANCOVA model will be repeated with missing data from subjects who discontinued aficamten treatment as if the aficamten subjects were in the placebo arm • Tipping point analysis 
Supportive analysis
 
 • Mixed model with numeric covariate as 0 for baseline and placebo group at Week 24 and 1 for aficamten group at Week 24, visit, stratification factors and stratification factors by visit as fixed term. unscheduled covariance structure will be specified. • Multivariate ANCOVA model to evaluate treatment by covariates interaction; ANCOVA model with significant covariates per model selection 
Subgroup analyses for variables in Section 7.5
	
 • Repeat the primary analysis after setting Week 24 pVO₂ to missing from subjects who were impacted by COVID pandemic • Summarize the number of subjects infected (positive COVID-19 test with or without symptoms) prior to Week 24 CPET.
Secondary estimand	ANCOVA model with fixed effects of treatment, randomization stratification factors baseline pVO ₂ value and baseline body weight.	Subgroup analyses for variables in Section 7.5	

Table 6: Endpoint Summary Table (Continued)

Endpoint	Primary Analysis Method	Sensitivity/Subgroup Analysis	COVID-19 Related Analyses
Secondary Endpoints			
Change in KCCQ-CSS from baseline to Week 12 and Week 24	MMRM model with baseline as covariate, randomization stratification factors, visit, treatment group, and interaction terms of treatment by visit and baseline by visit. An unstructured covariance matrix will be specified.	Sensitivity analysis: 
 Intermittent missing data be imputed using multiple imputation MCMC first and the monotone missing values will be imputed using the imputation model built from the placebo group. Complete data will be analyzed using ANCOVA model for each week separately. Subgroup analyses for variables in Section 7.5	
Change in post-Valsalva LVOT-G from baseline to Week 12 and Week 24	MMRM model with baseline as covariate, randomization stratification factors, visit, treatment group, and interaction terms of treatment by visit and baseline by visit. An unstructured covariance matrix will be specified.	Sensitivity analysis: 
 Intermittent missing data be imputed using multiple imputation MCMC first and the monotone missing values will be imputed using the imputation model built from the placebo group. Complete data will be analyzed using ANCOVA model for each week separately, Subgroup analyses for variables in Section 7.5	
Proportion of patients with ≥ 1 class improvement in NYHA Functional Class from baseline to Week 12 and Week 24	CMH test stratified by randomization factors	Treating patient as non-responder if NYHA is not performed and repeat CMH test. Subgroup analyses for variables in Section 7.5	

Table 6: Endpoint Summary Table (Continued)

Endpoint	Primary Analysis Method	Sensitivity/Subgroup Analysis	COVID-19 Related Analyses
Proportion of patients with post-Valsalva LVOT-G <30 mmHg	CMH test stratified by randomization factors	Subgroup analyses for variables in Section 7.5	
Total duration of SRT eligible during the 24-week of treatment period	Total duration of SRT eligible during the 24-week of treatment period will be analyzed using an ANCOVA model includes treatment and randomization stratification factor beta blocker use/non-use as fixed effects and significant baseline characteristics as covariates. Stepwise model selection method will be used based on the default stay or entry level of 0.05 to evaluate significant baseline covariates.	SRT eligible will be assigned value of 1 and SRT not eligible will be assigned value of 0. Area under the curve using the numeric value assigned and treatment duration until Week 24 will be calculated. AUC will be analyzed using the same ANCOVA model. Same ANCOVA model will be used to analyze the total time for SRT eligibility.	
Change in total workload during CPET from baseline to Week 24	Missing data will be imputed using multiple imputation method (Section 7.7.1). Complete dataset will be analyzed using an ANCOVA model with fixed effects of treatment, randomization stratification factors baseline total workload value and baseline body weight.	Sensitivity analysis 
 • ANCOVA model will be repeated with missing data from subjects who discontinued aficamten treatment as if the aficamten subjects were in the placebo arm. • Tipping point analysis Subgroup analyses for variables in Section 7.5	

¹See [Table 5](#) for details on the two estimands for the primary endpoint.

